7.15.3 Posttreatment PARS

PARS assessments will be completed at posttreatment for each family by central assessors at FIU, BU, or BMC who are masked to treatment assignment.

7.15.4 Retention and Study Compensation

Based on similar studies conducted in usual care settings that do not provide free study treatment, we expect roughly 30-50% attrition by the final follow-up timepoint, and roughly 10% of data points to be missing with each collected timepoint. REDCap surveys will be configured to minimize missing values (e.g., requiring participants to complete each item, or explicitly indicate “refuse to answer” before proceeding to the next item; providing real time alerts to the data management team when items or entire forms are missing). Data will additionally be checked on a weekly basis by a research supervisor, and patterns of missingness will be identified and corrected in real time throughout the study. To further reduce instances of missing data, we have kept the number of study forms to a minimum in order to minimize the burden to participants, and participants will be provided compensation for their time completing study forms. Finally, participants will be compensated for the burdens of completing study assessments (see below).

Given the aim to evaluate treatment engagement and performance under typical circumstances, families are not compensated for participating in treatment. To ensure generalizability and observe the treatment comparators under natural conditions, treatment is not funded by the study nor offered for free. Rather, treatment is to be paid for via the natural channels of payment in the participating health centers (e.g., insurance and co-payments). In contrast, families are compensated for participation in study assessments that are not part of the treatment comparators under study. Specifically, families will receive the following compensations for completing various study assessment components:

- a. \$50 for baseline assessment (staggered payments: \$25 following baseline questionnaires and \$25 following baseline PARS completion)
- b. \$25 for midtreatment assessment
- c. \$50 for posttreatment assessment
 - i. \$30 additional compensation for completing posttreatment PARS assessment
- d. \$100 for completing follow-up assessment

*Coaches (who are not guardians) will not receive compensation for the assessments they complete. Compensation will only be provided to the youth and guardian informants. One ClinCard that will be loaded with the above payments will be given to each family for each child enrolled in the study.

Automatic email reminders and weekly emails and phone calls from Kids FACE FEARS staff members should be used to increase participation in study assessments. Families who do not complete the baseline assessment are not randomized. Families who do not complete

their assigned treatment are still invited to complete all subsequent evaluations (i.e., midtreatment, posttreatment, and follow-up evaluations).

FIU will run weekly reports to see which participants have completed their assessment and send this report to BMC. The lead site RA will load the appropriate compensation amount onto the participant's ClinCard as each of the assessment points is complete.

7.16 Statistical Considerations

Study results will be reported according to CONSORT guidelines.

7.16.1 Sample size determination. Power analysis to determine the appropriate sample size for the trial had to take into account data clustering and repeated measurements. Study data were clustered in multiple ways, resulting in non-independent observations and inflated type I error. First, there were multiple observations per child due to the repeated measures design with four major assessment points. Second, there was additional clustering due to multiple children from each site. The intraclass correlation (ICC) is a quantitative estimate of clustering and allows for adjustment for non-independence. Study investigators estimated an ICC of .5, meaning it was anticipated that 50% of the variation in the observations would be due to differences between individuals and between sites (the remaining 50% of the variation was assumed to be due to individuals varying in their responses over time). The design effect (DE) reflects the extent to which standard errors are deflated if clustering is ignored. The DE is equal to $1 + (m - 1) \times \text{ICC}$, where m is the number of repeated measures. Accordingly, with 4 time points and an assumed ICC of .5, the design effect was calculated to be 2.5. Any sample size estimate must be multiplied by 2.5 in order to obtain a sample size appropriate for the observed clustering while maintaining nominal alpha and power levels.

The required study sample size was calculated via conventional methods for repeated measures / mixed models analysis. Required sample size is a function of the alpha (type I error rate) and beta (1 – power) values. Required size per group is: $n = 2 * (Z_{1-\alpha} + Z_{1-\beta})^2$. Before adjusting for the DE, these computations found $n=60$ was required in each group for an $\alpha=.05$ (assuming family-wise error rates=.05 across the study to account for multiple comparisons) and $\text{power}=.8$ (corresponding to $\beta=.2$). After adjusting for the DE of 2.5, this power analysis indicated $n=150$ was required per group (60×2.5), for a total of $N = 300$.

The needed sample size of $N = 300$ (outlined above) was based on the primary comparative effectiveness tests of this study (Aim I). That said, a sensitivity analysis was also conducted to evaluate the magnitude of effects that could be detected in moderation analyses

examining heterogeneity of treatment effects (Aim II). These analyses were conducted with G*power using the repeated measures analysis of variance (ANOVA) test. Repeated measures ANOVA is similar to a mixed model in some respects, but simpler and uniformly less powerful⁸⁰ using the repeated measures ANOVA, therefore, offers a conservative estimate of the effects able to be detected with each mixed model. With $N = 300$, $\alpha = .05$, power = .8, two treatment conditions, four measurements, and a correlation between repeated measures of .5, the trial was powered to detect moderation effects as small as Cohen's $d = 0.068$. This is 7% of a SD difference and a very small effect.

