6.3 Study Population

6.3.1 Number of Participants. Power analysis (accounting for an expected attrition and missing data) indicated we require 150 participants per group, for a total of 300 participants in the study.

6.3.2 Eligibility Criteria. The study eligibility and inclusion, and exclusion criteria for families include:

Inclusion/ Eligibility

- Elevated child/adolescent anxiety - Operationalized as T-Score on the PROMIS Pediatric Short Form-Anxiety Scale v2.0 ≥ 55 (Child eligible if *either* the Pediatric Self-Report *or* the Parent Proxy Report score was ≥ 55)
- Child aged 7-18 years (inclusive) at time of screening
- Child and caregiver(s) are fluent in English or Spanish
- If taking medication for emotional problems, child must be on a stable dose (Operationalized as no adjustments to prescription for ≥ 8 weeks)

Exclusion Criteria

- Severity requiring higher level of care, as defined by any of the following:
 - Suicidal thoughts or behaviors (STB) with *active* plan or STB(s) that required a higher level of care within the past 6 months (e.g., inpatient, partial hospitalization)
 - Anxiety-related absences $\geq 50\%$ of school days over the past month (If summer, attendance during last month of previous school year considered)
 - Substance use that required emergency services or inpatient/partial hospitalization within past 3 months

- Clinician determined child requires higher level of care than outpatient services
- History of diagnosed autism spectrum disorder or intellectual disability with severe challenges and needs for support (e.g., complete absence of verbal communication unrelated to anxiety)
- Currently engaged in CBT or planning to continue different therapy for anxiety during study treatment phase
- Child is a ward of the state

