7.16.2 Handling of Missing Data

7.16.2.1 Prevention and monitoring. All study data will be collected via electronic capture and communication directly with the study team. Based on similar studies conducted by our group and in related research in similar settings, we expect roughly 10% of data points to be missing. REDCap surveys will be configured to minimize missing values (e.g., requiring participants to complete each item, or explicitly indicate "refuse to answer" before proceeding to the next item; providing real time alerts to the data management team when items or entire forms are missing). Data will additionally be checked on a weekly basis by a research supervisor, and patterns of missingness will be identified and corrected in real time throughout the study. To further reduce instances of missing data, we have kept the number of study forms to a minimum in order to minimize the burden to participants, and participants will be provided compensation for their time completing study forms. Finally, participants will be compensated for the burdens of completing study assessments at a rate of \$50 for baseline assessments (including PARS) and, \$25 for midtreatment assessments, \$50 for posttreatment assessments (including PARS), \$100 for week 52 assessments and \$30 for completion of PARS at posttreatment (note: compensation will not be provided for completion of measures that will be included as part of routine care). Coaches will not receive compensation for the assessments they complete.

7.16.2.2 Statistical handling of missing data. All analyses will consist of intention-to-treat models drawing on all available data. To account for missing data, we will employ multiple imputation. Recommended procedures for single and multilevel multiple imputation will be conducted using BLIMP software, using fully conditional specification multiple imputation (FCS-MI). For each model, 50 datasets with imputed values will be created using other model covariates as predictors of missingness. Model convergence will be assessed across 8 Markov Chain Monte Carlo (MCM) processes and verified for potential scale reduction (PSR) factor<1.05. Main analyses will be conducted on the imputed dataset and the results will be pulled for final estimates (using R 4.4.1 mitml for imputation pooling per Rubin's rules, and lme4 for multilevel models, or lm and glm for linear and logistic regression models).

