7.16.3 Covariates

Covariates for each model will include site, language of care, youth age, youth gender, youth race, youth ethnicity, and family resource insecurity (see Measures)

7.16.4 Primary analyses: Comparative effectiveness analyses. For primary analyses on continuous outcomes that were measured across the 4 major timepoints (e.g., caregiver- and youth-reports on the PROMIS Anxiety Scale, CALIS), mixed models of change¹⁴⁴ will be run separately for each outcome. Mixed models are preferred for longitudinal designs because they allow for individual estimates of change and have robust power in the presence of missing data and attrition.^{145,146} Covariates for each model will include site, language of care, youth age, youth gender, youth race, youth ethnicity, and family resource insecurity (see Measures), and any other baseline variables found to significantly differ across participants in the two conditions. The random effects of intercept (reflecting individual variation in mean outcome level) will be assessed. The fixed effects of Treatment Condition, Time, and the Treatment \times Time interaction will be analyzed in the prediction of change. We will examine non-linear models of change (i.e., log transformations of Time), which afford examination of symptom trajectories across time that are not gradual and incremental (e.g., steep improvements during initial weeks of treatment, followed by a slowing down of improvements toward the end of treatment, and then relative stability across the follow-up time interval). To aid interpretation of the meaningfulness of between-group differences, Cohen's d 's will be computed for each continuous outcome on model means at post and follow-up.

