For primary analyses on the dichotomous categorical outcomes PARS Treatment Responder Status at posttreatment, baseline PARS scores will be examined for each participant to determine their individual thresholds for classification as Treatment Responders (i.e., 35% PARS score reduction). These thresholds will be used to classify each participant's statuses as posttreatment. Logistic regression models will examine Treatment Condition (along with the study covariates) as a predictor of Treatment Responder Status and Remission Status at post. For primary analyses on continuous outcomes of Treatment Satisfaction at post, linear regression models will examine Treatment Condition (with the study covariates) as a predictor of caregiver- and youth-reported posttreatment satisfaction.

7.16.5 Heterogeneity of treatment effects. For Aim II analyses (heterogeneity of treatment effects) predictor and moderator terms will be added to the models predicting youth anxiety severity that were outlined above. For study covariates being considered as predictors/moderators (e.g., language of care, youth age, youth gender, youth race, youth ethnicity, and family resource security), this will entail only adding interaction terms, as the main effects of these variables will already be in the models. For the additional variables considered as treatment moderators that are not already included as model covariates (e.g., caregiver nativity) this will entail adding main effects and interaction terms to the models. For each model examining heterogeneity of treatment effects, the relevant terms of interest will be the 2-way interaction of Variable \times Time (reflecting whether the variable uniformly predicted change across the two treatments) and the 3-way interaction of Variable \times Treatment Condition \times Time (reflecting whether the variable moderated treatment effects; i.e., whether the variable predicted differential response across the treatments). As with the Aim I comparative effectiveness analyses, log transformations of Time will be entered to consider non-linear models of change. Significant interactions will be followed up with post-hoc probing on subgroups to clarify the nature and direction of interaction, and results will be plotted for visual depiction.

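### The derivation of N = 300 is wrong as written: the formula has no effect size and does not give 60, a repeated-measures design effect is multiplied onto children, and the claimed attrition allowance does not exist

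*Combined protocol and SAP*

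**What the plan says.** Section 7.16.1 describes the required size as depending on alpha and beta, and prints n per group = 2 × (Z for alpha + Z for power)². With alpha .05 and power .8 it reports: "Before adjusting for the DE, these computations found $n=60$ was required in each group". The .05 is qualified by "assuming family-wise error rates=.05 across the study to account for multiple comparisons", but no per-test alpha is given and sidedness is not stated.

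The same section defines a design effect of 1 + (m − 1) × ICC, with m the number of repeated measures. Four time points and an ICC of .5 give 2.5, and the text adds: "Any sample size estimate must be multiplied by 2.5 in order to obtain a sample size appropriate for the observed clustering". Hence 60 × 2.5 = 150 per group and 300 in total.

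On losses, three places matter:
- 6.3.1: "Power analysis (accounting for an expected attrition and missing data) indicated we require 150 participants per group"
- 7.15.4: "we expect roughly 30-50% attrition by the final follow-up timepoint", plus about 10% of data points missing at each timepoint
- 7.16.2.1: "we expect roughly 10% of data points to be missing", without the attrition figure

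The planned primary analyses (7.16.4) are of two kinds. Repeatedly measured outcomes get mixed models with a Treatment × Time term: "We will examine non-linear models of change (i.e., log transformations of Time". Single-timepoint outcomes get ordinary regressions, for example "Logistic regression models will examine Treatment Condition (along with the study covariates) as a predictor of Treatment Responder Status".

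**The concern.** A sample size for comparing two means cannot be computed from alpha and beta alone. Without a target difference, 80% power is a statement about nothing in particular. No effect size or SD for the Aim I comparison appears anywhere in the document. The only effect size in the sample-size section, 0.068, is given for the Aim II moderation analyses.

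The design effect has a separate problem. A factor defined on measurements per child converts a number of independent observations into a number of correlated observations. It does not convert children into more children. It also does not correspond to a test of Treatment × Time, and it has no meaning for PARS response or satisfaction analysed at one timepoint.

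Finally, 6.3.1 tells readers that losses were allowed for. Aim I covers longer-term as well as acute effectiveness, so Week 52, where losses are expected to be greatest, belongs to the primary objective. If the trial finds no difference between two active CBT formats, readers will need to know what difference it could have detected, and the plan does not tell them.

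**Working it through.** **Step 1: the printed formula.** Inputs from 7.16.1: alpha .05, power .8 (z = 0.842). Sidedness is not stated, so both are tried.

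- One-sided: 2 × (1.645 + 0.842)² = 12.37
- Two-sided: 2 × (1.960 + 0.842)² = 15.70
- Two-sided .01 (family-wise .05 split equally over the five primary outcome domains in 6.2.1, as an illustration): 2 × (2.576 + 0.842)² = 23.36

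None is near 60. Dividing by d² restores the usual formula. The d that yields 60 is then:

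| Alpha | d for n = 60 |
|---|---|
| .05 one-sided | √(12.37/60) = 0.454 |
| .05 two-sided | √(15.70/60) = 0.511 |
| .01 two-sided | √(23.36/60) = 0.624 |

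**Step 2: the design effect.** The later arithmetic does reproduce: 1 + 3 × 0.5 = 2.5; 60 × 2.5 = 150; 150 × 2 = 300. The unit is what fails. Sixty independent observations inflate to 150 correlated observations, which at four per child is 150/4 = 37.5, about 38 children per group. Multiplying 60 children by 2.5 therefore overstates the need, so this error is conservative.

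**Step 3: attrition.** The product 60 × 2.5 uses up all 150, so the allowance is zero. At 30% and 50% attrition, 150 × 0.7 = 105 and 150 × 0.5 = 75 per group remain at Week 52.

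**Step 4: what N = 300 can detect in the planned mixed model (illustration).** Assumptions: 150 per group; compound symmetry with correlation .5 (the plan's own ICC); total SD 1; visits at Weeks 0, 8, 20 and 52 (the latest midtreatment and posttreatment invitation weeks and the follow-up week in 7.1); time entered as log(week + 1); fixed effects for arm, time and arm × time; monotone dropout with cumulative loss of 10/20/30% or 17/33/50% at the three later visits. The dropout patterns are assumed; only their endpoints come from 7.15.4.

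Detectable difference = (z for alpha + 0.842) × SE × log(week + 1), where SE is the generalised-least-squares standard error of the interaction, log 21 = 3.045 and log 53 = 3.970. For example, with no loss at Week 52: 2.802 × 0.02777 × 3.970 = 0.309.

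| Loss by Week 52 | SE | Week 20 / Week 52, alpha .05 | Week 20 / Week 52, alpha .01 |
|---|---|---|---|
| None | 0.02777 | 0.237 / 0.309 SD | 0.289 / 0.377 SD |
| 30% | 0.03065 | 0.261 / 0.341 SD | 0.319 / 0.416 SD |
| 50% | 0.03341 | 0.285 / 0.372 SD | 0.348 / 0.453 SD |

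**Step 5: PARS response.** Two-proportion pooled formula, two-sided, 80% power, with the roughly 60% CBT response rate quoted in 7.2 as the reference arm. The 120 and 100 per arm follow from 20% and 33% lost by posttreatment in the same dropout patterns.

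| Per arm | Detectable rate against 60%, alpha .05 | Alpha .01 |
|---|---|---|
| 150 | 43.9% | 40.4% |
| 120 | 42.0% | 38.1% |
| 100 | 40.3% | 36.0% |

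**The case against.** The strongest reply is that N = 300 is probably adequate. At the implied d of 0.511 (two-sided .05, one timepoint), power is about 96% with 105 per group and 88% with 75. On that view this is a reporting defect in a trial whose size survives its own worst attrition figure. The calculation stands, and it is why no change to N is proposed. But 0.511 is back-calculated and stated nowhere, so it cannot support the claimed power, and it does not make the attrition statement in 6.3.1 true.

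A denominator may have been lost when the PDF was read. That is possible, but the sentence before the formula also names only alpha and beta, and no Aim I effect size appears elsewhere.

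Section 7.16.1 also contains a four-measurement sensitivity calculation giving 0.068. It is assigned to Aim II moderation and gives no detectable difference for Aim I.

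The illustrative figures do depend on assumptions. Posttreatment is triggered by completing treatment, so it may come before Week 20: visits at Weeks 0/5/10/52 give 0.19 SD at posttreatment and 0.32 SD at Week 52 with no loss. Correlations of .3 to .7 move the no-loss Week 52 figure from 0.37 to 0.24 SD. The separate 10% of missing data points is not included. Five domains undercounts the tests, because several outcomes have both caregiver and youth versions. The 60% reference comes from another trial, and the plan does not say it used the 35% PARS reduction. These points qualify the size of the illustration and leave the three defects untouched.

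**Conclusion.** The concern holds in all three parts and must be fixed. The printed formula gives 12.4 or 15.7 rather than 60. The factor of 2.5 is applied to the wrong unit. The attrition allowance asserted in 6.3.1 is contradicted by the arithmetic in 7.16.1. These conclusions rest on the document's own text and figures.

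The trial is not shown to be underpowered, because the design-effect error overstates the need while the missing attrition step understates it. What fails is the justification: 80% power is claimed for no stated difference, and one power statement cannot describe outcomes and timepoints that differ this much. Under the assumptions in the working, the detectable difference at two-sided .05 is 0.24-0.285 SD at Week 20 and 0.31-0.37 SD at Week 52 across no loss to 50% dropout. For PARS it is 60% against 44% with 150 per arm, or against 40-42% with 20-33% lost.

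The 10% missing-data figure and the 30-50% attrition figure are different quantities and do not contradict each other.

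**What to change.** Keep N = 300 and issue a dated correction to 7.16.1 that:

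1. States the effect size and sidedness originally used, and how the family-wise .05 is divided among the primary tests.
2. Replaces the multiplication by 2.5 with a power calculation or simulation for the planned random-intercept, log-time mixed model, and adds a separate one for the single-timepoint PARS test.
3. Reports the detectable difference at posttreatment and at Week 52, with no loss and with 30-50% attrition, and lists the assumptions on correlation, visit timing and dropout pattern.

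In 6.3.1, delete or correct the statement that attrition and missing data were accounted for. In 7.16.2.1, add the 30-50% attrition expectation beside the 10% per-timepoint figure; this last change is editorial.

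The cost is a text correction and a re-run calculation, with no extra patients and no change to design or analysis. The drawback is that the detectable difference at one year will look less favourable, more so once multiplicity is applied.

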Table 1. Specific Aims of the Kids FACE FEARS Trial

Aim	Domain	Objective
Aim I	Comparative Effectiveness	To compare the acute and longer-term effectiveness of Therapist-Led CBT (telehealth, office-based, or hybrid) versus Guided Online CBT (with minimal clinician involvement) for treating youth anxiety identified in pediatric healthcare.
Aim II	Heterogeneity of Treatment Effects	To determine whether key factors predict or moderate differential treatment engagement or response, in turn informing treatment personalization for various patient subgroups.
Aim III	Implementation Facilitators and Barriers	To explore quantitative and qualitative data to understand perspectives, preferences, background factors, clinical and treatment engagement variables, and organizational factors that impede or facilitate implementation of, and patient engagement with, the comparators in pediatric health settings.

Note: Kids FACE FEARS=Kids Formats of Anxiety Care Effectiveness study For Extending the Acceptability and Reach of Services

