4.1 Primary Objective

The objective of Aim 1 (*Comparative Effectiveness*) is to compare the acute and long-term effectiveness of Therapist-Led CBT (telehealth, office-based, or hybrid) vs Guided Online CBT (with minimal clinician support) for treating youth anxiety identified in pediatric healthcare. It is hypothesized that youth in both conditions would show significant curvilinear improvements over time characterized by relatively steep improvements during the beginning and middle of the treatment phase, followed by a slowing down of improvements toward the end of treatment and then relative stability across the follow-up time interval. Comparative effectiveness analyses will

compare differences in outcome slopes across the two conditions. Aim 1 focuses on the following primary treatment outcomes across the comparators: family-rated anxiety severity, family-rated anxiety-related life impairment, independently rated treatment responder and anxiety remission status, family perceived effectiveness, and family satisfaction with care. Data on a range of secondary outcomes are also collected.

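### The plan assumes a study-wide family-wise error rate of .05, but the primary analysis section names no procedure that would deliver it over seven (or eight) separately modelled primary variables

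*Combined protocol and SAP*

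**What the plan says.** The only statement on multiplicity is in section 7.16.1 (Sample size determination). It enters alpha .05 and power .8, "assuming family-wise error rates=.05 across the study to account for multiple comparisons", reaches 60 per group, multiplies by a design effect of 2.5, and arrives at 150 per group and 300 in total. The same section ties that total to the Aim I primary comparisons.

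Section 7.16.4 (Primary analyses) sets out those comparisons:

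- For the repeated continuous measures (PROMIS anxiety and CALIS, caregiver and youth), mixed models "will be run separately for each outcome". The fixed effects are Treatment Condition, Time and their interaction. Section 4.1 says the comparison will "compare differences in outcome slopes across the two conditions".
- For the PARS: "Logistic regression models will examine Treatment Condition (along with the study covariates) as a predictor of Treatment Responder Status and Remission Status at post".
- For satisfaction: "linear regression models will examine Treatment Condition (with the study covariates) as a predictor of caregiver- and youth-reported posttreatment satisfaction".

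No alpha level, adjustment, order or lead outcome appears in 7.16.4. The moderation sensitivity calculation in 7.16.1 uses alpha .05 again, also without adjustment.

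**The concern.** A family-wise rate of .05 is a property of a set of tests and a decision rule taken together. The plan states the property but gives neither a closed list of tests nor a rule. A reader of the results could reasonably believe that the chance of any false difference between formats was held at 5%, when nothing prespecified would have held it there.

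If an adjustment were chosen at analysis, then the family, the method and the place of remission, perceived effectiveness and CGI-I could all be settled after the between-arm results were known. The trial is meant to tell families and health systems which CBT format works better, so a claim of superiority on one of several outcomes should carry the error rate that the plan advertises.

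**Working it through.** **The plan's own figure.** Design effect = 1 + (4 − 1) × .5 = 2.5; 60 × 2.5 = 150 per group; 2 × 150 = 300. These steps reproduce. The 60 does not: the printed formula, 2 × (Z₁₋α + Z₁₋β)², has no effect-size term and gives 12.4 with a one-sided Z or 15.7 with a two-sided Z. The 60 therefore cannot show whether an adjusted alpha was used. The text states .05 and no divisor.

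**Count of tests with a model in 7.16.4.** PROMIS × 2, CALIS × 2, PARS response × 1, satisfaction × 2 = 7. Remission makes 8. It is called primary in 4.1, 6.2.1 and 7.6.1 and is modelled in 7.16.4, but it is absent from the synopsis list, the 6.2.1 bullets and Table 3, and no section gives its threshold. Seven is the firm count. Table 3 also lists caregiver perceived effectiveness and CGI-I (caregiver and youth) as primary, but 7.16.4 writes no model for them.

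**Chance of at least one false claim.** Assumptions: every test at two-sided .05, no true difference on any outcome, normal test statistics. The documents give no correlations between outcomes, so these are assumed and varied.

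Independent tests (the upper bound): 1 − .95⁷ = .302; 1 − .95⁸ = .337.

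One common correlation r, by numerical integration of 1 − ∫ φ(u) [Φ((1.96 − √r·u)/√(1 − r)) − Φ((−1.96 − √r·u)/√(1 − r))]ᵏ du:

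| r | k = 7 | k = 8 |
|---|---|---|
| .3 | .27 | .30 |
| .5 | .23 | .25 |
| .7 | .18 | .19 |
| .9 | .11 | .12 |

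A pattern closer to this trial lets correlation depend on who reports and on what. It was evaluated by simulation, with a response–remission correlation of .7 to .9 for the eighth test:

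| same informant / same domain, other informant / neither | k = 7 | k = 8 |
|---|---|---|
| .5 / .3 / .2 | .26 | .28–.29 |
| .6 / .4 / .3 | .24 | .26–.27 |
| .7 / .5 / .4 | .22 | .23–.24 |

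The range is therefore about 22–29%. No case tried comes down to 5%.

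**What adjustment would cost in stated power.** Assume that 60 per group reflects two-sided .05 and 80% power. Then d = √(15.70/60) = 0.51, and the expected test statistic is 0.5115 × √(60/2) = 2.80.

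- k = 7: alpha = .05/7 = .00714, critical value 2.69, power = Φ(2.80 − 2.69) = 54%.
- k = 8: alpha = .05/8 = .00625, critical value 2.73, power = Φ(2.80 − 2.73) = 53%.

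This is the Bonferroni level, which is also Holm's first and most stringent step; later Holm steps are easier.

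**The case against.** The strongest reply is that the gap is one of specification, not of demonstrated inflation. Section 7.16.4 never says each test is judged at .05, and the one study-level statement points away from that. This stands. A reader might infer that the plan runs at a 22–34% error rate; the documents do not support that, and the figures describe only what follows if .05 is applied test by test.

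A reader might also infer that the count is 10 or 11, by adding perceived effectiveness and the two CGI-I reports. Table 3 calls them primary, but 7.16.4 has no test for them, so they do not belong in the main figure.

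Nor do the effect sizes add tests. Cohen's d "will be computed for each continuous outcome on model means at post and follow-up", but the plan offers this as an aid to interpretation and attaches no test to it. Aim I (Table 1) does set out "To compare the acute and longer-term effectiveness of Therapist-Led CBT" against the online format, yet sections 4.1 and 7.16.4 point to the Treatment × Time interaction as the comparison for the repeated measures.

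It may be said that the outcomes are correlated and that section 7.6 chooses several domains on purpose. Both are true. Correlation reduces the excess without removing it, and the reason for measuring several domains does not address error control. That reason does mean that a single primary outcome need not be demanded.

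**Conclusion.** The point holds as an inconsistency between a stated error-rate property and an analysis section with no means of delivering it. Seven primary variables are tested separately, eight if remission is kept and defined. The size, about 22–29%, is conditional on testing each at two-sided .05, on no true difference anywhere, and on correlations that are assumed. Independence gives 30–34% and a uniform correlation of .9 gives 11–12%; both are extremes for outcomes from caregiver, youth and masked evaluator.

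The power figure of 53–54% rests on an effect size inferred from n = 60, not stated in the plan. A reader might take it as proof that 300 participants are too few. The documents do not support that, because the effect size and the alpha behind the 60 are unknown. The collected data stay fully usable, and the matter should be settled before any between-arm primary comparison is run.

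**What to change.** In 7.16.4, list the Aim I primary between-arm tests: Treatment × Time for PROMIS and CALIS by informant, and Treatment Condition for the posttreatment PARS and satisfaction outcomes. State whether remission (with its threshold), perceived effectiveness and CGI-I belong to the family. Then take one of two routes:

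1. Control the listed family at two-sided .05 by a named procedure, for example Holm. In 7.16.1, limit the family-wise statement to that family and restate power at the adjusted alpha, giving the assumed effect size.
2. Delete the family-wise statement from 7.16.1 and say in 7.16.4 that the primary tests are reported unadjusted.

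Date the change. Both routes need only text; neither needs new data or added enrolment. Deciding which tests form the family is a substantive choice for the sponsor. Route 1 costs stated power per test, to about 53–54% at its most stringent step under the assumption above. Route 2 leaves the possible 22–29% in place but discloses it.
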